8.4.3. Analysis of Secondary Efficacy Endpoints

Change from baseline in number of disease-related hospitalization days per 28 days and change from baseline in occurrence/recurrence of status epilepticus per 28 days are the two key secondary endpoints. The treatment groups will be compared using Wilcoxon Rank-Sum Test. Number of disease-related hospitalization days and number of occurrence/recurrence of status epilepticus will be tabulated by frequency and percent as well.

Percent change from baseline in total seizure frequency per 28 days will be analyzed in a similar way to the primary endpoint.

Response rates (25%, 50%, 75%, and 100%) for motor seizure and total seizure will be tabulated by treatment groups and treatment will be compared by Cochran-Mantel-Haenszel test adjusting for stratifying factor.

Number of disease-related emergency room visits and in-patient hospitalizations, number of rescue seizure medications, and seizure clusters will be tabulated by frequency and percent. In addition, change from baseline in disease-related emergency room visits and in-patient hospitalizations per 28 days, and change from baseline in seizure clusters per 28 days will be summarized.

Health-related quality of life, as measured by the CarerQoL-7D questionnaire, will be summarized descriptively.

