3.5. Baseline

For safety endpoints, baseline for double-blind period and open-label period will be defined as the last measurement prior to or on the date of first dose date.

For efficacy endpoints during double-blind period, baseline is defined as the 28 days prior to randomization. Baseline definition for the seizure frequency, disease-related hospitalization days, and occurrence/recurrence of status epilepticus per 28 days will be calculated as the number of seizures, hospitalization days, and status epilepticus, respectively, during the run-in period, divided by the number of days in the run-in period, and multiplied by 28. Only “valid days” will be used in the calculation of seizure frequency per 28 days. A “valid day” is defined as a day where seizure counts information is present.

For summary, based on on-vatiquinone period, the baseline will be defined as the last measurement prior to the first dose of vatiquinone. ie, the last assessment prior to first dose in subjects with treatment sequence vatiquinone/vatiquinone, or the last assessment prior to first open-label vatiquinone in subjects with treatment sequence placebo/vatiquinone. For subjects who are randomized to placebo group in double-blind period and enter into the open-label period, all assessments conducted on the day they take last dose of double-blind period drug will be considered as baseline for the on-vatiquinone period.

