5.1. Primary Endpoint(s) Analysis

5.1.1. Definition of Endpoint(s)

The percent change in the motor seizure frequency per 28 days in the double-blind period in the ITT population will be the primary efficacy endpoint.

Motor seizure frequency will be counted across the entire 24 weeks (168 days) of the double-blind treatment period. Seizure frequency will be normalized to 28 days to allow for comparison of seizure frequency in the double-blind period to the seizure frequency observed during the 28-day run-in period. The 28-day run-in period will be used to establish the baseline seizure frequency.

During the study, subjects (and/or their parent/legal guardian) were required to record occurrence of seizures in a seizure diary on a daily basis. A blank entry in the seizure diary would be considered an invalid day; it is not considered to be an absence of seizures. Only days that have seizure diary information completed are considered to be valid entry days.

For calculation of the primary endpoint, the total number of motor seizures collected on valid entry days will be divided by the number of valid entry days and then multiplied by 28 to provide the average number of seizures normalized “per” 28 days. The formula to calculate this is shown below:

$$\text{Seizure frequency per 28 days during DB period} = \frac{\text{Total number of reported motor seizures during DB period}}{\text{Number of “valid” days with reported motor seizures during DB period}} \times 28$$

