5.1.2. Primary Analysis

For primary analysis, both the motor seizure frequencies per 28 days in the pre-randomization period as well as the percentage change in motor seizure frequencies per 28 days in the double-blind period will be rank transformed separately.

The analysis of covariance (ANCOVA) will then be conducted on this rank transformed data with treatment, and stratifying factor and the ranked pre-randomization phase seizure frequency per 28 days as a covariate. P-values will be computed between active and placebo treatment groups.

Due to an expected irregular distribution of seizure frequency, median will be the primary statistic of interest for the primary endpoint. The difference in median of the percent change from baseline between the two treatment groups will be estimated using Hodges-Lehmann estimator along with 95% CI for understanding the treatment effect size.

The stepwise approach to estimate the median difference of percent change using Hodges-Lehmann estimator is:

- a. derive the seizure frequency per 28 days for baseline (BL) and double-blind (DB) period.
- b. calculate the percent change from baseline as $100 \times (DB - BL)/BL$.
- c. apply the below SAS code of PROC NPAR1WAY nonparametric model to generate Hodges Lehmann Estimator:

```
*** Hodges Lehmann Estimator;  
proc npar1way data=<dataset name> HL ;  
  class <treatment variable name>;  
  var <percent change from baseline variable name>;  
  ods select HodgesLehmann;  
run;
```

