5.2. Secondary Endpoint(s) Analysis

5.2.1. Key/Confirmatory Secondary Endpoint(s)

The key secondary efficacy endpoints of the study are as follows:

- Number of disease-related hospitalization days
- Occurrence or recurrence of status epilepticus

For the key secondary endpoints, if subject is without any events at baseline, ie, no hospitalization or status epilepticus at baseline, then subject will be considered as having 0 events at baseline.

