5.2.1.1. Number of Disease-Related Hospitalization Days

Number of disease-related hospitalization days per 28 days will be calculated as the total number of disease-related hospitalization days multiplied by 28 and divided by the total number of days in the interval.

Disease related hospitalization is defined as any hospitalizations occurring as the consequence of an AE or SAE during the study period that is related to the subject's disease state or baseline conditions of the subject and lack of alternative explanation for the event. All the hospitalization events will be reviewed, classified as disease-related or not and agreed upon prior to the study unblinding.

The change from baseline in number of disease-related hospitalization days per 28 days during the double-blind period will be compared between the treatment groups using Wilcoxon rank-sum test for ITT population.

The number and the change from baseline in number of disease-related hospitalization days per 28 days during the double-blind period will be summarized descriptively for ITT population. Number of disease-related hospitalization days will be tabulated by frequency and percent as well for double-blind period, respectively, for ITT.

In addition, the change from baseline in number of disease-related hospitalization days per 28 days will also be summarized descriptively for the following subgroups for double-blind period for ITT population.

- Age group (<8 years old vs ≥ 8 years old)
- Sex (Male vs Female)
- Race (White vs Other)
- Region (United States vs Rest of the World)

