5.2.1.2. Number of Occurrence/Recurrence of Status Epilepticus

Number of occurrence/recurrence of status epilepticus per 28 days will be calculated as the total number of status epilepticus multiplied by 28 and divided by the total number of days in the interval.

The change from baseline in the number of occurrence/recurrence of status epilepticus per 28 days during double-blind period will be compared between the treatment groups using Wilcoxon rank-sum test for ITT.

The number of subjects who had status epilepticus and the number and the change from baseline in the number of occurrence/recurrence of status epilepticus per 28 days will be summarized for double-blind period for ITT population. Number of occurrence/recurrence of status epilepticus will be tabulated by frequency and percent as well for double-blind period, for ITT population.

In addition, the number and the change from baseline in the number of occurrence/recurrence of status epilepticus per 28 days will also be summarized descriptively for the following subgroups for double-blind period, for ITT population.

- Age group (<8 years old vs ≥ 8 years old)
- Sex (Male vs Female)

- Race (White vs Other)
- Region (United States vs Rest of the World)

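### Both key secondary endpoints are tested with an unstratified Wilcoxon on change from a noisy 28-day baseline that is not used as a covariate: valid, but a potential loss of power

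*SAP*

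**What the plan says.** SAP 5.2.1.1: the change in disease-related hospitalization days per 28 days "will be compared between the treatment groups using Wilcoxon rank-sum test for ITT population". SAP 5.2.1.2: the change in status epilepticus per 28 days "will be compared between the treatment groups using Wilcoxon rank-sum test for ITT". Protocol 8.4.3 has the same test: "The treatment groups will be compared using Wilcoxon Rank-Sum Test". None of the three names a stratum or covariate.

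On the baseline, SAP 3.5 states: "For efficacy endpoints during double-blind period, baseline is defined as the 28 days prior to randomization". For a subject with no run-in events, SAP 5.2.1 adds: "then subject will be considered as having 0 events at baseline".

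The primary analysis (SAP 5.1.2) is a rank ANCOVA "with treatment, and stratifying factor and the ranked pre-randomization phase seizure frequency per 28 days as a covariate". Total seizure frequency (SAP 5.2.2.1) follows the primary method, and the responder comparison (SAP 5.2.2.2) is a Cochran-Mantel-Haenszel test adjusted for stratum. Under SAP 3.8 and 3.10 only two strata remain, Leigh syndrome and Other. SAP 3.6 places the two key secondaries, and no other secondary endpoint, in the fixed sequence after the primary, each at two-sided 0.05.

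**The concern.** Of the treatment comparisons tested in SAP 5.1 and 5.2, only the two alpha-controlled secondaries leave out the stratum, and the SAP gives no reason.

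The larger issue is the change score. A rate from a short window is subtracted in full from a rate over a window six times as long. One status epilepticus event in the run-in moves the change by 1 per 28 days; one event on treatment moves it by 1/6. A subject with a single run-in event therefore tends towards the low end of the ranking whichever arm they are in. A covariate model estimates how much weight the baseline deserves instead of fixing it at one.

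At stake is power in a trial of about 30 per arm. The second key secondary is tested only if the first succeeds, so a weak first test also limits the second.

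**Working it through.** **The plan's own power figure.** Power is stated only for the primary endpoint: 81% (Protocol 8.2) and 80% (SAP 1.4), for 30 per arm, difference 40, SD 50, Wilcoxon. By Noether's formula p = Φ(0.8/√2) = 0.714, and power = Φ(√(3 × 60) × (0.714 − 0.5) − 1.96) = 82.0%. That agrees with both. There is no corresponding figure for either key secondary.

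**Noise in the baseline.** Inputs: a 28-day run-in (SAP 3.5) and 168 days of double-blind treatment (SAP 5.1.1), a ratio of 6. With the same rate L per 28 days in both periods and Poisson counts:
- variance of the run-in rate = L
- variance of the double-blind rate = 6L/6² = L/6
- ratio = 6, so the run-in supplies L/(L + L/6) = 6/7, or 86%, of the Poisson variance of the change.

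The ratio does not depend on how rare the events are.

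**Power simulation.** From the documents: 30 per arm, the two windows, two strata, two-sided 0.05. Assumed: gamma-Poisson events, 50% rate reduction, frailty variance 0.5 or 2, 30% of subjects with Leigh syndrome, stratum rate ratio 1 or 2, mean hospital stay 5 days. There were 1,500 runs per scenario, so the standard error is at most √(0.25/1500) = 1.3 points. The planned Wilcoxon on change is compared with rank ANCOVA on change, with stratum and the ranked own run-in rate. Power (%) at stratum rate ratio 1:

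| Events per 28 days | Frailty variance | Subjects with zero run-in | Hospital days: planned / rank ANCOVA / gain | Status epilepticus: planned / rank ANCOVA / gain |
|---|---|---|---|---|
| 0.05 | 0.5 | 95% | 13.9 / 17.4 / 3.5 | 13.5 / 17.5 / 4.0 |
| 0.15 | 0.5 | 87% | 23.1 / 33.9 / 10.8 | 22.7 / 37.6 / 14.9 |
| 0.4 | 0.5 | 69% | 29.5 / 48.9 / 19.4 | 26.1 / 58.1 / 32.0 |
| 1.0 | 0.5 | 44–45% | 38.7 / 66.5 / 27.8 | 40.6 / 83.9 / 43.3 |
| 0.05 | 2 | 95% | 10.8 / 13.9 / 3.1 | 11.4 / 15.8 / 4.4 |
| 0.15 | 2 | 88% | 15.5 / 19.7 / 4.2 | 14.1 / 19.5 / 5.4 |
| 0.4 | 2 | 74% | 22.8 / 28.5 / 5.7 | 20.7 / 32.0 / 11.3 |
| 1.0 | 2 | 58% | 31.3 / 39.9 / 8.6 | 35.9 / 54.9 / 19.0 |

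At stratum rate ratio 2 and frailty variance 0.5, the gains at 0.4 and 1.0 events were 17.4 and 24.9 points for hospital days, and 29.1 and 42.7 for status epilepticus.

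**Smaller effect.** The primary's planning assumption of 50% against 10% decreases gives 1 − 50/90 = 44% relative reduction. At 44%, rank ANCOVA on change matched or beat the planned test in 31 of 32 scenarios, with gains of about 0 to 35 points. The exception, 14.6% against 15.8%, is within simulation error.

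**Stratum alone.** A van Elteren test on change, which adds only the stratum, differed from the planned test by −1.4 to +0.6 points. With a stratum rate ratio of 5 the difference was −2.4 to +1.6 points.

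**Where the loss arises.** For hospital days at 0.15 events and frailty variance 0.5, a Wilcoxon on the double-blind rate with no subtraction had 37.1% power, against 23.1% as planned.

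**Type I error** (2,000 null runs, frailty variance 2). Planned test 3.8% to 5.2%; rank ANCOVA on change 4.6% to 5.1%.

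**The case against.** The strongest reply is that the planned test is pre-specified, identical in Protocol and SAP, and holds its error rate. All of that stands. A reader might infer a validity problem or inflated alpha from the missing stratum; the null runs and the fixed sequence in SAP 3.6 show neither.

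A reader might also infer that baseline is thrown away. It is not: each endpoint's own run-in rate is calculated (SAP 3.5) and subtracted. Nor is it the baseline in the primary model, which is motor seizure frequency.

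It is tempting to think the problem is worst when events are sparse. The table shows the opposite. At 0.05 events per 28 days 95% of subjects have a zero run-in, so their change equals the on-treatment rate and little is lost. Power is then under 20% with either test, and the choice of model is not the main limitation.

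Finally, subtraction can help when stable differences between subjects are large. For hospital days at 1.0 events and frailty variance 2, the Wilcoxon had 31.3% power on change and 24.9% on the double-blind rate alone. Even rank ANCOVA on the double-blind rate fell below the planned test in one high-dispersion case at a 44% reduction (22% against 27%, status epilepticus at 1.0 events). This does not defend the unadjusted test, but it is a good reason to keep change as the outcome.

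**Conclusion.** The point holds as one of efficiency. Both key secondaries use a valid but unadjusted test on a change score dominated by run-in noise, and the plan already has a better form of model in its primary analysis.

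The gain from rank ANCOVA on change is about 0 to 5 points when events are rare (0.05 per 28 days) or dispersion is very high. With a 50% reduction, low dispersion and 0.4 to 1.0 events per 28 days, it is about 17 to 28 points for hospitalization days and 29 to 43 for status epilepticus. Almost all of it comes from using baseline as a covariate. The case for the stratum is consistency with the randomisation and the primary model, not power.

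A flat statement that the plan loses much of its power on these endpoints would go too far. The documents give no event rate, dispersion, effect size or power for either endpoint, so every figure here rests on assumed values.

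**What to change.** Before unblinding, amend SAP 5.2.1.1 and 5.2.1.2:
- Keep the Protocol's variable, change from baseline per 28 days.
- Rank it, and rank the run-in rate of the same endpoint separately.
- Test treatment by ANCOVA on the ranked change, with stratum (Leigh/Other) and the ranked run-in rate as covariates.
- Keep the Wilcoxon test on change as a supportive analysis.
- Record the departure from Protocol 8.4.3 in SAP 3.10, and state the event rates and power assumed for each endpoint.

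If the sponsor prefers the unadjusted test, the SAP should say why and give the same assumptions.

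No new data are needed. The cost is a documented change to a pre-specified confirmatory test, made after the stratum composition of the enrolled subjects is known (SAP 3.10), with little gain if the events turn out to be rare. If unblinding has already taken place, the Wilcoxon should remain the confirmatory test and the rank ANCOVA be reported as supportive.

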5.2.1.2. Number of Occurrence/Recurrence of Status Epilepticus

Number of occurrence/recurrence of status epilepticus per 28 days will be calculated as the total number of status epilepticus multiplied by 28 and divided by the total number of days in the interval.

The change from baseline in the number of occurrence/recurrence of status epilepticus per 28 days during double-blind period will be compared between the treatment groups using Wilcoxon rank-sum test for ITT.

The number of subjects who had status epilepticus and the number and the change from baseline in the number of occurrence/recurrence of status epilepticus per 28 days will be summarized for double-blind period for ITT population. Number of occurrence/recurrence of status epilepticus will be tabulated by frequency and percent as well for double-blind period, for ITT population.

In addition, the number and the change from baseline in the number of occurrence/recurrence of status epilepticus per 28 days will also be summarized descriptively for the following subgroups for double-blind period, for ITT population.

- Age group (<8 years old vs ≥ 8 years old)
- Sex (Male vs Female)

- Race (White vs Other)
- Region (United States vs Rest of the World)

5.2.2. Supportive Secondary Endpoint(s)

5.2.2.1. Total Seizure

Percent change from baseline in total seizure frequency per 28 days will be analyzed in a similar way to the primary endpoint for double-blind period for ITT population.

Change from baseline and percent change from baseline in total seizure frequency per 28 days will also be summarized descriptively for double-blind period for ITT population.

Change from baseline and percent change from baseline in total seizure frequency per 28 days, will also be summarized descriptively by disease subtype and age group for double-blind period for ITT population.

- Age group (<8 years old vs ≥ 8 years old)

In addition, the seizure frequency per 28 days will be summarized by type: motor seizure or non-motor seizure during double-blind.

5.2.2.2. Responder Rate

Response rate of x% is defined as the proportion of subjects whose seizure frequency change per 28 days is more than x% compared to baseline. Response rates (>30%, 30% to -30%, < -30% to -60%, > -60% to -100%) for motor seizure and total seizure will be summarized for double-blind period by treatment groups. Where negative values indicate a decrease in seizures from baseline and positive values indicate an increase in the number of seizures from baseline.

Response rates during double-blind period will be compared between two treatment groups by Cochran-Mantel-Haenszel test adjusting for stratifying factor for ITT population.

In addition, the response rate of -50% in both motor seizure and in total seizure in last 12 weeks of double-blind period will be compared similarly for ITT population.

Responder rates for motor seizure and total seizure will also be summarized descriptively for double-blind period for ITT population.

- Age group (<8 years old vs ≥ 8 years old)

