3.10. Changes of Analysis from Protocol

There are no major changes in analysis from study protocol.

At the time of study design and enrollment, the initial plan of randomization and stratification was planned based on the disease subtype to include the following:

1. Alpers/DNA polymerase subunit gamma (POLG)
2. Leigh syndrome
3. Mitochondrial encephalomyopathy, lactic acidosis, and stroke-like episodes (MELAS) and
4. Other genetically confirmed mitochondrial disease secondary to mitochondrial mutation.

However, due to the challenges in identifying and enrolling participants who meet the inclusion and exclusion criteria for the study, there was a disparity in enrollment of subjects with the prespecified subtypes mentioned in the protocol (listed above). Only one subject was randomized for Alpers/(POLG) and no subjects were randomized for MELAS. Therefore, the only strata in the ITT population will be Leigh syndrome and “Other” (Section 3.8).

Considering the patient population currently enrolled into the study, we have pre-specified two specific mitochondrial disease subtypes, in addition to Leigh syndrome, that are of interest and in whom we seek to understand treatment effect independent of those recorded in the overall population. These additional disease subtypes are pontocerebellar hypoplasia type 6 (PCH6) secondary to arginine-tRNA synthetase 2 (RARS2) mutation and mt-aaRS2 disorders (for all mitochondrial aminoacyl tRNA synthetase disorders which includes subjects with RARS-2 mutations associated with PCH6 mutation). All analyses planned for the overall population will be repeated for Leigh syndrome, PCH6, and mt-aaRS2 disorders.

In the protocol, the secondary end point related to the change in motor seizures and total seizures was planned to be analyze in proportion of subjects with $\geq 25\%$, $\geq 50\%$, $\geq 75\%$, and 100% reduction. This proportion of change does not capture disease progression and potential increase in seizures. Therefore, the analysis groupings were changed to reflect the proportion of subjects with $>30\%$, 30% to -30% , $< -30\%$ to -60% , $> -60\%$ to -100% for motor seizure and total seizures will be summarized for double-blind period by treatment groups.

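### The SAP's responder rule and deepest response category are mis-signed, and its four bins replace the Protocol's 25/50/75/100% reduction rates, which they cannot reproduce

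*SAP*

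**What the plan says.** Protocol 2.2.2 lists, among the other secondary endpoints, the proportions of subjects with reductions of at least 25%, 50% and 75%, and of 100%, for motor and for total seizures. Protocol 8.4.3 gives the analysis: "Response rates (25%, 50%, 75%, and 100%) for motor seizure and total seizure will be tabulated by treatment groups", with the arms compared by a Cochran-Mantel-Haenszel (CMH) test adjusted for the stratifying factor. Protocol 8.4.9 asks for the same rates by disease subtype, descriptively. Section 8.4.3 names no window. Section 8.4.8 rests formal conclusions on the double-blind period, so I read these as 24-week rates.

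SAP 1.2.2 keeps the responder objective, but the endpoint list in SAP 1.3.2 omits the thresholds. In SAP 5.2.2.2 a response rate of x% "is defined as the proportion of subjects whose seizure frequency change per 28 days is more than x% compared to baseline". The categories follow: "Response rates (>30%, 30% to -30%, < -30% to -60%, > -60% to -100%) for motor seizure and total seizure will be summarized". The sign rule is then given: "Where negative values indicate a decrease in seizures from baseline and positive values indicate an increase in the number of seizures from baseline". The arms are compared by CMH, and a further comparison is planned for "the response rate of -50% in both motor seizure and in total seizure in last 12 weeks of double-blind period".

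SAP 3.10 opens with "There are no major changes in analysis from study protocol". It then discloses the new groupings, with the same fourth category, and gives the reason: "This proportion of change does not capture disease progression and potential increase in seizures".

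**The concern.** There are two separate faults.

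The first is direction. SAP 5.1.2 computes percent change as double-blind minus baseline over baseline, so improvement is negative. A rule that counts changes *more than* x%, applied to x = -50, selects the subjects on the wrong side of the cut. The sign of the fourth category fails in the same way. A rule fixed in advance and tested between arms should not need a programmer to guess its intent.

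The second is removal. The SAP plans no 25%, 50%, 75% or 100% reduction rate over the full double-blind period. Only the 50% cut remains, for the last 12 weeks. A seizure-free subject is pooled with one at -61%. A subject at -29%, who meets the Protocol's 25% threshold, shares a category with one at +29%. SAP 2 and 3.10 repeat all analyses in Leigh syndrome, PCH6 and mt-aaRS2 disorders, so both faults carry into each subtype.

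**Working it through.** **1. The plan's own figure.** Protocol 8.2 gives 81% power (SAP 1.4: 80%) for 30 per arm, difference 40, SD 50, two-sided 0.05, Wilcoxon test. By the Noether formula, p = Φ(40/(50√2)) = Φ(0.566) = 0.714. Power = Φ(√(12 × 60 × 0.25) × (0.714 - 0.5) - 1.96) = Φ(0.914) = 82.0%. A t-test with n × 0.864 gives 80.6%. The stated figure is reproduced and is not in dispute. No power is stated for the responder analysis.

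**2. The definition, read literally.** Set x = -50 and count a subject if change > -50.

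| Percent change | At least 50% reduction (Protocol) | SAP rule, literal |
|---|---|---|
| -100 | yes | no |
| -80 | yes | no |
| -55 | yes | no |
| -50 | yes | no |
| -45 | no | yes |
| 0 | no | yes |
| +50 | no | yes |

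The literal rule is the exact complement. Setting x = +50 does not help: it counts subjects who worsened by more than 50%.

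**3. The categories.** The fourth requires a value above -60 that extends down to -100. No value satisfies both, so subjects below -60% have no category. The other three are signed correctly, and the strict inequalities place each boundary once: +30 and -30 in the second category, -60 in the third.

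**4. Can the Protocol rates be recovered from the bins?** Correct the fourth sign and let n1 to n4 be the counts in one arm of N subjects, from worst to best.

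- 25%: the cut falls inside the second bin, so the rate is known only to lie between (n3 + n4)/N and (n2 + n3 + n4)/N.
- 50%: inside the third bin, so between n4/N and (n3 + n4)/N.
- 75% and 100%: inside the fourth bin, so between 0 and n4/N.

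None is identified by the table.

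**5. Size, as an illustration only.** Inputs are the planning means -10% and -50% and SD 50% (Protocol 8.2). Normality is my assumption.

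- At least 50% reduction: placebo Φ((-50 + 10)/50) = Φ(-0.8) = 21.2%; vatiquinone Φ(0) = 50.0%.
- Literal rule: 1 - 0.212 = 78.8% and 1 - 0.500 = 50.0%, which appears to favour placebo.
- Below -60%, uncategorised if the fourth bin is taken literally: Φ(-1.0) = 15.9% and Φ(-0.2) = 42.1%.
- Step 4 bounds on the 50% rate: 15.9% to 34.5% on placebo (Φ(-0.4) = 34.5%) and 42.1% to 65.5% on vatiquinone (Φ(0.4) = 65.5%).

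The normal model puts 3.6% of placebo and 15.9% of vatiquinone subjects below -100%, which cannot occur.

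**The case against.** The intent can be inferred. SAP 5.2.2.2 states the sign rule, and a response rate of -50% under a responder heading can sensibly mean only a reduction. The likely outcome is a programming query, not a reversed table, and the four-category summary does not use the *more than* rule. This stands as a limit on the likely harm. The text still specifies the complement.

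The change is open and was made under blind. SAP 3.10 gives it a reason. SAP 1 requires finalization before the first lock, SAP 3.4 places unblinding after that lock, and Protocol 5.3 keeps the sponsor blinded until all subjects complete the placebo-controlled phase. Because SAP 3.10 also reports who was enrolled, a reader might infer that outcomes shaped the cut points. Nothing in the documents supports that.

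A reader might also infer that the results are lost. SAP 3.2 provides subject listings of source data, from which any threshold rate can be derived. What is missing is the planned table and test.

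Adjoining categories both name -30% and -60%, so overlap might be suspected. Step 3 shows there is none.

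Finally, restoring the thresholds adds tests: 4 thresholds × 2 seizure types = 8, or 8 × 4 = 32 if repeated in three subtypes. That is a fair point and limits the fix.

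**Conclusion.** The concern holds on both counts. The definition sentence gives the complement of a responder rate when x is negative, and the fourth category is empty as signed, in SAP 5.2.2.2 and again in 3.10. These are matters of logic and rest on no assumption. The Protocol's reduction rates over the double-blind period are planned nowhere in the SAP and cannot be reconstructed from the new bins. Wanting to show worsening justifies one more category; it does not justify dropping the planned ones.

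The contrast of 79% and 50% against 21% and 50% shows direction and rough size. It should not be read as a forecast. The plan itself expects an irregular distribution, and the planning means describe 24 weeks whereas the only -50% comparison covers the last 12.

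The consequence is confined to a supportive secondary endpoint. It lies outside the fixed sequence in SAP 3.6, so the family-wise error rate and the primary and key secondary conclusions are untouched. It should be corrected, but it does not threaten the trial's main inference.

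**What to change.** - In SAP 5.2.2.2, define response at level x as percent change ≤ -x%, and word the last-12-weeks comparison as a reduction of at least 50%.
- Correct the fourth category to below -60% down to -100% in SAP 5.2.2.2 and 3.10. Leave the other categories and boundaries as they are.
- Restore the Protocol's ≥25%, ≥50%, ≥75% and 100% reduction rates over the double-blind period, with the stratified CMH test, for motor and total seizures in the overall ITT population. In disease subtypes report them descriptively only, as in Protocol 8.4.9.
- Keep the four new categories as an added display, so that worsening above 30% is shown.

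The cost is SAP wording, one more table, and eight nominal tests that are not adjusted for multiplicity and should be labelled so. No new data are needed: the percent changes are already derived for the primary and total-seizure analyses.
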